3.1.1.2. D^2 Phase 2 Portion

The Phase 2 will use a Simon 2-stage design to determine the efficacy and safety of D² (Simon, 1989).

D² Simon Stage 1

Once the RP2D is confirmed, a cohort of 32 subjects (including subject enrolled in the safety run-in portion) will be enrolled at the RP2D to determine the safety and preliminary efficacy of D^2 .

D² Simon Stage 2

If the threshold for minimum overall response rate (ORR) is met in Stage 1, an additional 68 subjects will be enrolled to further confirm the safety and efficacy of D² at the RP2D.

3.1.1.3. Addition of Pomalidomide Plus Dexamethasone to Daratumumab Plus Durvalumab Upon Progressive Disease

For all subjects enrolled into D^2Arm , upon confirmed PD, for subjects who have had at least 2 cycles of D^2 , POM + dex may be added to the D^2 regimen at the investigator's discretion.

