^c If DARA infusion rate reduction does not mitigate the toxicities, additional subjects may be enrolled using a reduced infusion rate starting with the first dose of DARA.

Study Population

The study population will consist of subjects with multiple myeloma who have received at least 3 prior lines of therapy including a proteasome inhibitor (PI) and an immunomodulatory agent or who are double-refractory to a PI and an immunomodulatory agent.

Length of Study

The study will consist of the following consecutive phases: Screening, Treatment, and Follow-up. The screening period may not exceed a 28-day window prior to start of study treatment (Cycle 1 Day 1). Subjects may continue on study treatment until PD or unacceptable toxicity. For subjects who have had at least 2 cycles of D², upon PD, at the investigator's discretion, POM + dex may be added to the D² regimen. All subjects will have an End of Treatment (EOT) Visit within 7 days after discontinuation of all study treatment. Subjects are to return to the study site 28 (+3) days after the EOT visit and 90 (+3) days after the last dose of DURVA or DARA for safety follow-up visits, and then, all subjects who received POM as part of study treatment, will be followed for second primary malignancies (SPMs) every 6 months until the end of the trial (once last subject completes the 90 day posttreatment follow-up visit).

The End of Trial is defined as either the date of the last visit of the last subject to complete the post-treatment follow-up, or the date of receipt of the last data point from the last subject that is required for primary, secondary analysis, as prespecified in the protocol, whichever is the later date.

Study Treatments

For subjects receiving D² regimen:

- Intravenous DARA at the assigned dose level (16 mg/kg) for Cycles 1 to 2 Day 1, 8, 15, 22/28-day cycle, Cycle 3 to 6 Day 1, 15 /28-day cycle, Cycle ≥ 7 Day 1/28-day cycle
- Intravenous DURVA at the assigned dose level (1500 or 750 mg) on Cycle 1 Day 2/28-day cycle then Cycle ≥ 2 on Day 1 or 2/28-day cycle

Overview of Key Efficacy Assessments

- Myeloma paraprotein
- Serum immunoglobulins
- Serum free light chains
- Corrected serum calcium
- Percent plasma cells in the bone marrow
- Radiographic assessments of lytic bone lesions
- Extramedullary plasmacytoma (EMP) assessments
- Response per International Myeloma Working Group (IMWG) criteria

Overview of Key Safety Assessments

- Complete physical examination including vital signs

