1. INTRODUCTION

On 05 Sep 2017, a Partial Clinical Hold was placed on this study by the United States (US) Food and Drug Administration (FDA). The decision by the FDA was based on data related to risks of anti-programmed cell death-1 (PD-1) antibody, pembrolizumab, in combination with immunomodulatory drugs (IMiDs®) in patients with multiple myeloma. As a result, enrollment into this study has been discontinued. Subjects who are receiving clinical benefit, based on the discretion of the investigator, may remain on study treatment after being reconsented.

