1.2. Compound Background

1.2.1. Durvalumab (MEDI4736)

Durvalumab (MEDI4736) (DURVA) is a human immunoglobulin G (IgG)1 kappa monoclonal antibody (mAb) directed against human programmed cell death ligand 1 (PD-L1) protein.

Refer to the durvalumab Investigator's Brochure (IB) for detailed information concerning the available pharmacology, toxicology, drug metabolism, clinical studies, and adverse event (AE) profile of the investigational product (IP).

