1.2.3. Pomalidomide

Pomalidomide (POM) is a novel drug in the class of immunomodulatory drugs known as IMiDs® compounds, and is structurally similar to thalidomide.

Refer to the POM IB for detailed information concerning the available pharmacology, toxicology, drug metabolism, clinical studies, and AE profile of the IP; as well as the current label (Pomalyst[®] PI; Imnovid[™] Summary of Product Characteristics [SmPC]).

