3.2. Study Duration for Subjects

The study will consist of the following consecutive phases: Screening, Treatment, and Follow-up. The screening period may not exceed a 28-day window prior to start of study treatment (Cycle 1 Day 1). Subjects may continue on study treatment until PD or unacceptable toxicity. For subjects who have had at least 2 cycles of D², upon PD, at the investigator's discretion, POM + dex may be added to the D² regimen. All subjects will have an End of Treatment (EOT) Visit within 7 days after discontinuation of all study treatment. Subjects are to return to the study site 28 (+3) days after the EOT visit and 90 (+3) days after the last dose of DURVA or DARA for safety follow-up visits, and then, all subjects who received POM as part of study treatment, will be followed for second primary malignancies (SPMs) every 6 months until the end of the trial (once last subject completes the 90-day post-treatment follow-up visit).

On 05 Sep 2017, a Partial Clinical Hold was placed on this study by the US FDA. The decision by the FDA was based on data related to risks of anti-PD-1antibody, pembrolizumab, in combination with IMiDs in patients with multiple myeloma. As a result, enrollment into this study has been discontinued. Subjects who are receiving clinical benefit, based on the discretion of the investigator, may remain on study treatment after being reconsented.

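### After the partial clinical hold, the protocol still permits pomalidomide plus dexamethasone to be added to durvalumab plus daratumumab at progression, and does not reconcile this with the hold text

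*Combined protocol and SAP*

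**What the plan says.** The hold is described at the head of the Protocol Summary, in Section 1 and in Section 3.2. Section 1 gives its basis: "The decision by the FDA was based on data related to risks of anti-programmed cell death-1 (PD-1) antibody, pembrolizumab, in combination with immunomodulatory drugs" in multiple myeloma. Two consequences follow in all three places. Enrollment has ended, and, in the words of Section 3.2, "Subjects who are receiving clinical benefit, based on the discretion of the investigator, may remain on study treatment after being reconsented".

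The option to add pomalidomide (POM) and dexamethasone (dex) at progression appears in four places: the Protocol Summary under Study Design and again under Length of Study, Section 3.1.1.3, and Section 3.2. Section 3.1.1.3 requires confirmed progressive disease (PD) and at least two cycles of durvalumab plus daratumumab (D²), after which "POM + dex may be added to the D^2 regimen at the investigator's discretion". Section 3.2 has the parallel statement: "upon PD, at the investigator's discretion, POM + dex may be added to the D² regimen".

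The protocol identifies both drug classes. Section 1.2.3 states: "Pomalidomide (POM) is a novel drug in the class of immunomodulatory drugs known as IMiDs". Section 1.2.1 describes durvalumab as a "monoclonal antibody (mAb) directed against human programmed cell death ligand 1 (PD-L1) protein", and Section 1.3.4 says that it stops PD-L1 from binding to PD-1.

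**The concern.** The hold concerns an antibody against PD-1 given with an IMiD. The retained option allows an IMiD to be newly started alongside an antibody that blocks the same pathway from the ligand side. The trigger is progression, while the hold text ties continued treatment to clinical benefit. An investigator with a progressing subject finds both statements in Section 3.2, and neither mentions the other. One site could read the hold paragraph as closing the option. Another could read the unqualified permission as leaving it open.

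At stake is a safety decision for subjects still on treatment, and whether each site takes it on the same basis. It also determines whether the POM + dex data, which Section 9.1 sets apart for separate analysis, can continue to accrue.

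**Working it through.** No arithmetic applies, because the plan gives no figure on this point. The check sets the current statements side by side.

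1. **Basis of the hold.** Section 1 refers to "risks of anti-programmed cell death-1 (PD-1) antibody, pembrolizumab, in combination with immunomodulatory drugs". The antibody named is pembrolizumab, against PD-1. Durvalumab is not named in that sentence.

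2. **Link to this regimen.** POM belongs to the drug class named in the hold (Section 1.2.3). Durvalumab acts on PD-L1 (Section 1.2.1) and so on the PD-1/PD-L1 axis (Section 1.3.4). The match is exact for the IMiD and by shared pathway for the antibody. The summary of Amendment 2 draws the same link: it says subjects are to be reconsented on safety concerns about a PD-1 pathway inhibitor with an immunomodulatory agent. That summary is used here as the sponsor's own reading of the hold, not as current text.

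3. **Condition for staying on treatment.** The three hold statements name clinical benefit, judged by the investigator, and reconsent. They do not say when benefit is judged, whether it is judged again at progression, or whether the reconsent covers a later start of POM.

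4. **Condition for adding POM + dex.** The four permission statements name progression, at least two cycles of D² and investigator discretion. Two of them require the progression to be confirmed (Protocol Summary under Study Design; Section 3.1.1.3). The other two say PD without that word (Protocol Summary under Length of Study; Section 3.2). None of the four names the hold, clinical benefit or reconsent.

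5. **Cross-references.** There are three hold statements and four permission statements. No cross-reference runs in either direction, including within Section 3.2, which contains one of each.

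6. **Supporting text.** The rest of the protocol treats the option as live. Section 1.3.4 still argues for exploring the addition. Table 4 keeps the rows for POM and dex dosing, and its footnote h sets hematology monitoring once POM has been added. Section 3.1.4 covers evaluability for dose-limiting toxicity after the addition. Tables 7 and 8 give POM dose modifications. None of these mentions the hold.

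7. **Progression against benefit.** Section 11.1 lists PD as a sufficient reason to stop treatment. Section 3.2 says treatment may continue until PD or unacceptable toxicity, and then gives the POM + dex option. So the protocol generally treats PD as the end of treatment, with this option as the exception, and it does not say how the exception sits with the benefit condition.

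8. **Effect on the analysis.** Section 9.1 analyses safety and efficacy data after the addition separately. The response rate for D² is therefore unchanged whichever way the point is settled.

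**The case against.** The strongest reply is that both sets of statements can be followed together. The hold is partial. Its stated consequences are that enrollment stopped and that subjects may stay on study treatment after reconsent. Section 6.3.1 and Table 4 count POM and dex as study treatment. A reconsent about combining a PD-1 pathway inhibitor with an IMiD is at least as consistent with an option kept open under disclosure as with an oversight. The benefit condition can be read as a gate at reconsent, with the option applying at a later event. Some relevant text is also not visible: Section 7.2.2.1.1 is cited but absent, Section 7.3 mentions an eligibility requirement for POM that does not appear, and the consent pages were removed.

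Much of this stands, and it rules out several stronger readings that a reader might infer:

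- **That the protocol breaches the hold.** The terms of the hold are not reproduced, and no visible text forbids the addition.
- **That the current text confines treatment to subjects with benefit.** The exclusive wording is in the summary of Amendment 2. The current sections say that such subjects may remain.
- **That durvalumab plus POM is what led to the hold.** The stated basis is pembrolizumab with IMiDs. Durvalumab shares the pathway but has a different target.
- **That progression rules out clinical benefit.** Benefit is undefined and left to the investigator. Under Appendix B, PD can be a laboratory finding: a 25% rise in serum M-component with an absolute increase of at least 0.5 g/dL.

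The reply does not remove the gap. If the option was deliberately kept open, no visible text says so. Missing text is unlikely to settle the matter, because the summary of Amendment 2 places its enrollment-stop changes in the Protocol Summary, Section 1 and Section 3.2. In their current form, the Protocol Summary and Section 3.2 carry the unqualified permission, and Section 1 does not address whether the option remains open. A restriction elsewhere would still leave four unqualified permissions in place.

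**Conclusion.** The point holds as an unreconciled tension on a safety matter, present within Section 3.2 and across the Protocol Summary and Sections 1 and 3.1.1.3. It is not a demonstrated contradiction or breach. The protocol should be amended because the decision concerns patient safety and the correction is cheap, although no statistical conclusion depends on it.

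The subjects concerned are those still on D² without POM who reach progression after at least two cycles. The documents do not give their number. It may be small, since enrollment is closed and the current version adopts toxicity guidelines dated 17 Nov 2020, about three years after the hold of 05 Sep 2017.

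A reader might also ask for the POM + dex displays to be split by start before or after the hold. The documents do not require this: the analyses are descriptive, and no endpoint or decision rests on such a split.

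The conclusion assumes that no text outside the supplied documents already gives sites a single instruction. If it does, the protocol should still be brought into line with it.

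**What to change.** Reconcile the hold text (Protocol Summary, Sections 1 and 3.2) with the POM + dex permission (Protocol Summary under Study Design and Length of Study, Sections 3.1.1.3 and 3.2, and Table 4 with its footnote h). Every place should give the same instruction on whether the addition remains open after the hold and, if so, under what conditions. That instruction should state how the benefit condition and the reconsent apply to a subject who progresses. The content of the rule is for the sponsor and the regulator, and none is proposed here.

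The cost is a wording amendment and a matching letter to sites. Sample size, endpoints and analyses do not change.

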3.1.3. Dose Review Team

[figure not shown]
The DRT consists of the Celgene medical monitor, Celgene lead safety physician, Celgene biostatistician, other Celgene functional area representatives, as appropriate, study-specific consultant(s) (MD/PhD), as required, and site investigator and/or designees who have enrolled subjects to the study.

The DRT members are responsible for all dosing decisions for the study. Dosing decisions may include de-escalation to a lower dose; continuation, delay, or termination of dosing, and repetition of or expansion of a cohort. All available safety and, if applicable,

Pharmacokinetic (PK), and preliminary efficacy data will be reviewed and can be considered in the DRT's decisions.

Dose Review Team meetings will be held to review all data, monitor safety, and make dosing and expansion decisions.

3.1.4. Dose-limiting Toxicity

• Receive at least 1 dose of study treatments within an assigned treatment arm and experience a DLT

• Receive at least 1 dose of study treatments and experience a DLT after POM + dex added

OR

• Receive 1 dose of DURVA and all DARA doses as per relevant treatment cycle, ≥ 16 doses of POM and ≥ 3 doses of dex and complete the safety follow-up through the end of the DLT evaluation period.

Nonevaluable subjects will be replaced.

Grading of DLTs will be according to the National Cancer Institute Common Terminology Criteria for Adverse Events (NCI CTCAE) Version 4.03.

A DLT will be defined as below:

Hematologic DLT

- a. Grade 4 neutropenia observed for greater than 5 days duration
- b. Grade 3 neutropenia associated with fever (≥ 38.5°C) of any duration.
- c. Grade 4 thrombocytopenia or Grade 3 thrombocytopenia with bleeding, or any requirement for platelets transfusion.
- d. Any other Grade 4 hematologic toxicity that does not resolve to subject's pretreatment baseline level within 72 hours
- e. Grade 4 anemia, unexplained by underlying disease.

Nonhematologic DLT

- a. Any nonhematological toxicity ≥ Grade 3 except for alopecia and nausea controlled by medical management
- b. Any treatment interruption greater than 2 weeks due to an AE.

While the rules for adjudicating DLTs in the context of dose escalation are specified above, an AE not listed above may be defined as a DLT after consultation with the sponsor and investigators, based on the emerging safety profile.

The study will be conducted in compliance with the International Council for Harmonisation (ICH) of Technical Requirements for Registration of Pharmaceuticals for Human Use/Good Clinical Practice (GCP) and applicable regulatory requirements.

Figure 1: Overall Study Design

D² Safety Run-in Phase (N =~6) Confirm tolerability of D² dose (3+3 design)

Figure 2: Study Schematic

Safety Follow-up -28 days post EOT -90 days post last dose of DURVa or DARA

3.2. Study Duration for Subjects

The study will consist of the following consecutive phases: Screening, Treatment, and Follow-up. The screening period may not exceed a 28-day window prior to start of study treatment (Cycle 1 Day 1). Subjects may continue on study treatment until PD or unacceptable toxicity. For subjects who have had at least 2 cycles of D², upon PD, at the investigator's discretion, POM + dex may be added to the D² regimen. All subjects will have an End of Treatment (EOT) Visit within 7 days after discontinuation of all study treatment. Subjects are to return to the study site 28 (+3) days after the EOT visit and 90 (+3) days after the last dose of DURVA or DARA for safety follow-up visits, and then, all subjects who received POM as part of study treatment, will be followed for second primary malignancies (SPMs) every 6 months until the end of the trial (once last subject completes the 90-day post-treatment follow-up visit).

On 05 Sep 2017, a Partial Clinical Hold was placed on this study by the US FDA. The decision by the FDA was based on data related to risks of anti-PD-1antibody, pembrolizumab, in combination with IMiDs in patients with multiple myeloma. As a result, enrollment into this study has been discontinued. Subjects who are receiving clinical benefit, based on the discretion of the investigator, may remain on study treatment after being reconsented.

3.3. End of Trial

The End of Trial is defined as either the date of the last visit of the last subject to complete the post-treatment follow-up, or the date of receipt of the last data point from the last subject that is required for primary, secondary analysis, as pre-specified in the protocol, whichever is the later date.

4. STUDY POPULATION

4.1. Number of Subjects

Up to approximately 144 subjects with RRMM will be enrolled worldwide.

• D² Cohort: Run-in cohort up to 18; Simon Stage 1 up to 26; Simon Stage 2 up to 68

4.2. Inclusion Criteria

Subjects must satisfy the following criteria to be enrolled in the study:

- 1. Subject received at least 3 prior anti-myeloma regimens including a PI and an immunomodulatory agent or is double-refractory to a PI and an immunomodulatory agent.
 - Induction, bone marrow transplant with or without maintenance therapy is considered one regimen
 - Refractory is defined as disease that is nonresponsive on therapy, or progresses within 60 days of last therapy. Nonresponsive disease is defined as either failure to achieve minimal response or development of progressive disease while on therapy.
 - For subjects who received more than 1 regimen containing a PI their disease must be refractory to the most recent PI containing regimen.
 - For subjects who received more than 1 regimen containing an immunomodulatory agent their disease must be refractory to the most recent immunomodulatory agent containing regimen.
- 2. Subject has measurable disease defined as:
 - a. M-protein (serum protein electrophoresis (sPEP) or urine protein electrophoresis (uPEP): $sPEP \ge 0.5 \text{ g/dL}$ or $uPEP \ge 200 \text{ mg/}24 \text{ hours}$) and/or
 - b. Light chain MM without measurable disease in the serum or the urine: serum immunoglobulin free light chain $\geq \! 10$ mg/dL and abnormal serum immunoglobulin kappa lambda free light chain ratio
- 3. Subject achieved a response (MR or better) to at least 1 prior treatment regimen
- 4. Subject has evidence of PD on or within 60 days of the most recent prior treatment regimen
- 5. Subject received an alkylating agent alone or in combination with other myeloma treatment
- 6. Subject has an Eastern Cooperative Oncology Group performance-status score of 2 or less
- 7. Subject's toxicities resulting from previous therapy (including peripheral neuropathy) have resolved or stabilized to ≤ Grade 1.
- 8. Subject is at least 18 years of age at the time of signing the informed consent form (ICF).

- 9. Subject must understand and voluntarily sign an ICF prior to any study-related assessments/procedures being conducted.
- 10. Subject is willing and able to adhere to the study visit schedule and other protocol requirements.
- 11. Females of childbearing potential (FCBP¹) must:
 - a. Have 2 negative pregnancy tests as verified by the investigator prior to starting study treatment. She must agree to ongoing pregnancy testing during the course of the study, and after end of study treatment. This applies even if the subject practices true abstinence from heterosexual contact.
 - b. Either practice true abstinence² from heterosexual contact (which must be reviewed on a monthly basis and source documented) or agree to use, and be able to comply with, effective contraception without interruption, 28 days prior to starting study treatment, during the study therapy (including dose interruptions), and for at least 90 days after discontinuation of study treatment.
 - c. Refrain from egg cell donation for at least 90 days after the final dose of DURVA or DARA, whichever is later.

12. Male subjects must:

- a. Either practice true abstinence² (which must be reviewed on a monthly basis) or agree to use a condom during sexual contact with a pregnant female or a female of childbearing potential while participating in the study, during dose interruptions and for at least 90 days following study treatment discontinuation, even if he has undergone a successful vasectomy.
- b. Refrain from sperm donation for at least 90 days after the final dose of DURVA or DARA, whichever is later.

4.3. Exclusion Criteria

The presence of any of the following will exclude a subject from enrollment:

- 1. Subject has had prior exposure to anti-CTLA-4, anti-PD-1, anti-PD-L1 mAbs, cell-based therapies (eg, CAR-T cells), or cancer vaccines
- 2. Subject received DARA or other CD38 antibodies therapies previously
- 3. Subject received any of the following within the last 14 days of initiating study treatment:
 - a. Plasmapheresis
 - b. Major surgery (as defined by the investigator)
 - c. Radiation therapy other than local therapy for myeloma associated bone lesions
 - d. Use of any systemic anti-myeloma drug therapy

¹ A female of childbearing potential (FCBP) is a female who: 1) has achieved menarche at some point, 2) has not undergone a hysterectomy or bilateral oophorectomy or 3) has not been naturally postmenopausal (amenorrhea following cancer therapy does not rule out childbearing potential) for at least 24 consecutive months (ie, has had menses at any time in the preceding 24 consecutive months)].

[figure not shown]
² True abstinence is acceptable when this is in line with the preferred and usual lifestyle of the subject. Periodic abstinence (eg, calendar, ovulation, symptothermal, post-ovulation methods) and withdrawal are not acceptable methods of contraception.

- 4. Subject received prior treatment with a monoclonal antibody within 5 half-lives of initiating study treatment
- 5. Subject used any investigational agents within 28 days or 5 half-lives (whichever is longer) of initiating study treatment
- 6. Subject is receiving concurrent chemotherapy or biologic or hormonal therapy for cancer treatment. Note: Concurrent use of hormones for noncancer-related conditions (eg, insulin for diabetes and hormone replacement therapy) is acceptable.
- 7. History of organ or allogeneic stem cell transplantation
- 8. Subject has received autologous stem cell transplantation (ASCT) within 12 weeks before the date of randomization.
- 9. Subject has any of the following laboratory abnormalities:
 - a. Absolute neutrophil count (ANC) $\leq 1,000/\mu L$
 - b. Platelet count: $< 75,000/\mu L$ (it is not permissible to transfuse a subject to reach this level)
 - c. Hemoglobin < 8 g/dL (< 4.9 mmol/L)(it is not permissible to transfuse a subject to reach this level)
 - d. Creatinine Clearance (CrCl) < 45 mL/min
 - e. Corrected serum calcium > 13.5 mg/dL (> 3.4 mmol/L)
 - f. Serum aspartate aminotransferase (AST) or alanine aminotransferase (ALT) $> 2.5 \times \text{upper limit of normal (ULN)}$
 - g. Serum total bilirubin $> 1.5 \times$ upper limit of normal (ULN) or > 3.0 mg/dL for subjects with documented Gilbert's syndrome
- 10. Subject has clinical evidence of central nervous system (CNS) or pulmonary leukostasis, disseminated intravascular coagulation, or CNS MM
- 11. Subject has known chronic obstructive pulmonary disease (COPD) with a forced expiratory volume in 1 second (FEV1) 50% of predicted normal. Note that FEV1 testing is required for subjects suspected of having COPD and subjects must be excluded if FEV1 is < 50% of predicted normal.
- 12. Subject has known moderate or severe persistent asthma within the past 2 years (see Appendix F) or uncontrolled asthma of any classification. Note that subjects who currently have controlled intermittent asthma or controlled mild persistent asthma are allowed to participate in the study.
- 13. Subject has plasma cell leukemia, Waldenstrom's macroglobulinemia, POEMS syndrome (polyneuropathy, organomegaly, endocrinopathy, monoclonal protein, and skin changes), or amyloidosis
- 14. Subject has nonsecretory MM
- 15. Subject has known allergy or hypersensitivity to study drug formulations
- 16. Subject has active or prior documented autoimmune or inflammatory disorders (including inflammatory bowel disease [eg, colitis, Crohn's disease], diverticulitis, celiac disease, irritable bowel disease, or other serious gastrointestinal chronic conditions associated

with diarrhea; systemic lupus erythematosus; Wegener syndrome; myasthenia gravis; Graves' disease; rheumatoid arthritis, hypophysitis, uveitis, etc) within the past 3 years prior to the start of treatment. The following are exceptions to this criterion:

- a. Subjects with vitiligo or alopecia.
- b. Subjects with hypothyroidism (eg, following Hashimoto syndrome) stable on hormone replacement.
- c. Psoriasis not requiring systemic treatment.
- 17. Subject has history of primary immunodeficiency
- 18. Subject is positive for human immunodeficiency virus (HIV), chronic or active hepatitis B or active hepatitis A or C.
- 19. Subject has received live, attenuated vaccine within 30 days prior to the first dose of DURVA (NOTE: Subjects, if enrolled, should not receive live vaccine during the study and 30 days after the last dose of DURVA)
- 20. Subject is currently using or has used immunosuppressive medication within 14 days prior to the first study dose of study treatment. The following are exceptions to this criterion:
 - a. Intranasal, inhaled, or local steroid injections (eg, intra-articular injection).
 - b. Systemic corticosteroids at physiologic doses not to exceed 10 mg/day of prednisone or equivalent.
 - c. Steroids as premedication for hypersensitivity reactions (eg, CT scan premedication).
- 21. Subject has any one of the following:
 - a. Clinically significant abnormal electrocardiogram (ECG) finding at screening
 - b. Congestive heart failure (New York Heart Association Class III or IV)
 - c. Myocardial infarction within 12 months prior to starting study treatment
 - d. Unstable or poorly controlled angina pectoris, including Prinzmetal variant angina pectoris
- 22. Subject has prior history of malignancies, other than MM, unless the subject has been free of the disease for ≥ 5 years with the exception of the following noninvasive malignancies:
 - a. Basal cell carcinoma of the skin
 - b. Squamous cell carcinoma of the skin
 - c. Carcinoma in situ of the cervix
 - d. Carcinoma in situ of the breast
 - e. Incidental histologic finding of prostate cancer (T1a or T1b using the TNM [tumor, nodes, metastasis] clinical staging system) or prostate cancer that is curative
- 23. Subject is a female who is pregnant, nursing, or breastfeeding, or who intends to become pregnant during the participation in the study.
- 24. Subject has significant medical condition, laboratory abnormality, or psychiatric illness that would prevent the subject from participating in the study

- 25. Subject has a condition including the presence of laboratory abnormalities, which places the subject at unacceptable risk if he/she were to participate in the study
- 26. Subject has a condition that confounds the ability to interpret data from the study

